**- PROTOCOL REVISION RECORD -**

**Original Protocol:** January 30, 2015 (Version 1.0)  
April 20, 2015 (Version 1.1)

**Revisions:**

[figure not shown]
Amendment #1:	February 7, 2016
Sections revised:	Schema, Sections 1-2, 3.9, 4-5, 6.2, 6.5-6.6, 7 (title only), 8.5.2, 8.5.3.1, 9.1, 10.2 (new), 11, 12.3, Appendix D, and Appendix E (removed).
Amendment # 2:	November 16, 2016
Sections Revised:	Title, Schema, Section 1, Section 2.3, Section 3.6, Section 4.1, Section 6, Section 9, Section 10, Section 12, Appendix D
Amendment # 3:	April 25, 2018
Sections Revised:	All to reflect change in dose
Amendment #4:	February 7, 2019
Sections Revised:	
Amendment #5:	October 4, 2019
Sections Revised:	Schema, Section 10 (Footnote #5), Appendix C, Exclusion Criteria
Amendment #5.1:	February 6, 2020
Sections Revised:	Change in PI (1st page, header, Appendix C)
Amendment #5.2:	June 10, 2020
Sections Revised:	DSMB
Amendment #5.3:	July 26, 2020
Sections Revised:	
Amendment #6:	October 21, 2022
Sections Revised:	Change in Statistician, first page, enrollment total updated to 15

## SCHEMA

### Eligible:

Women With HPV16-Associated Stage IB1-IV Cervical Cancer;  
Completed Definitive Treatment Within 12 Months.

### Study Design:

Treatment Groups/Cohorts					
Group	TA-CIN Route of Administration	Volume (mL)	Dose (µg)	Treatment Frequency/Weeks	# of Patients
1	Intramuscular Arm	0.53	100	3 administrations per subject; Weeks 1, 5, and 9	7
2	Intramuscular Thigh				7

## 1. SUMMARY

This is a randomized, multi-center, open label pilot study. The primary goal of this study is to determine the safety of TA-CIN vaccine as adjuvant therapy, and to assess evidence of induction of HPV antigen-specific immunologic response when administered at different locations. TA-CIN has proven to be well-tolerated in healthy humans when administered three times monthly intramuscularly in the deltoid at a 533 $\mu$ g dose. In this pilot study, a single dose level (100 $\mu$ g) assessment of the safety and tolerability of administering TA-CIN vaccine three times to either the arm versus the thigh of patients who have previously been treated for HPV16-related cervical cancer in the past year and are documented to have no evidence of disease recurrence based on standard-of-care imaging and/or clinical assessment upon eligibility. Since TA-CIN administration is likely to have low toxicity, an important element of this study is to analyze immunologic parameters to examine whether one of the two immunization sites induces greater HPV-specific immunogenicity. The immunogenicity analyses include: 1) assessment of T cell-mediated immune responses of peripheral blood lymphocytes to HPV16 E7E6 stimulation by ELISPOT, and if not discriminatory then 2) by T cell proliferation assays, or 3) by measurement of HPV16 L2E7E6-specific antibodies by ELISA (**Section 10**). These analyses will be combined with toxicity data to select a vaccination site for a future clinical trial(s).

A total of 15 patients will be enrolled to assess the safety of TA-CIN vaccine via different injection sites as adjuvant therapy. Patients with HPV16-associated stage IB1-IV cervical cancer who completed definitive cancer treatment within 1 year before the initiation of vaccination and are documented to have no evidence of disease recurrence based on standard-of-care imaging and/or clinical assessment will be eligible. This population was chosen because women with HPV-associated cervical cancer may potentially benefit from the vaccination strategy as adjuvant therapy as compared to healthy volunteers with respect to prevention or delay in the development of HPV16 associated cervical cancer recurrence. One dose level of TA-CIN (100 $\mu$ g) delivered via one of two different intramuscular injection sites is planned (**Section 6**).

Safety assessments will continue for a period for 1 month after the last vaccination; reporting requirements, exclusions, and stopping rules are outlined (**Sections 7 and 8**). Subjects who withdraw from the study for reasons other than toxicity may be replaced at the discretion of the Principal Investigator and/or IND sponsor.

Few or no serious adverse events (SAEs) are expected from this regimen and routes of administration. The motivation for the design is to confirm that the dose and site of injection implemented here has minimal or no systemic toxicity, as well as determining the preferred injection site that can elicit more potent immune response.

Patient immune and clinical responses in cohorts with different injection sites will be evaluated through the following methods: 1) peripheral blood lymphocytes (PBL) to assess HPV16 E6 and E7-specific CD8 $^{+}$  T cell ELISPOT and lymphocyte proliferative responses to HPV16 antigenic stimulation and T cell receptor sequencing; 2) serum for HPV16 L2, E6, and E7 and neutralizing antibody responses; 3) plasma for residual HPV viral load; and, 4) imaging scans per standard-of-care (i.e., every 6-12 months) and as clinically indicated to assess time to disease recurrence.

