### 2.3 Exploratory Objective(s)

- 2.3.1 To evaluate the levels of circulating HPV16 E6- and E7-specific CD8+ T cells in the peripheral blood pre- and post-vaccination using T cell receptor sequencing
- 2.3.2 To evaluate the levels of HPV-specific neutralizing antibodies in the peripheral blood pre- and post-vaccination
- 2.3.3 To assess residual HPV16 viral load in plasma
- 2.3.4 To assess time to disease recurrence as a measure of clinical response that may be associated with vaccine-induced immune responses

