### 3.7.2 Site of Vaccination Affects the Anti-Tumor Immunity

In another pre-clinical study, we explored whether the site of vaccination will impact anti-tumor immunity, specifically whether intramuscular vaccination of the leg will generate better anti-tumor immunity than vaccination on the arm against cervical HPV disease. As a model for vaccination of cervical cancer patients in the arm versus the leg, we vaccinated mice bearing cervicovaginal, luciferase-expressing TC-1 tumor with a therapeutic HPV16 DNA vaccine pNGVL4A-CRT/E7(detox), administered either in the front leg (which drains to a lymph node distal to the cervical tumor) or the hind leg (which drains to the proximal lymph node shared with the cervical tumor).

[figure not shown]

**Figure 3. Characterization of therapeutic antitumor effect of therapeutic HPV vaccine administered at different site in cervicovaginal tumor model.** 5~8 weeks old female C57BL/6 mice (5 mice/group) were injected with  $5 \times 10^4$  of TC-1/ luciferase cells at the intravaginal cavity on day 0. The mice were vaccinated with 20  $\mu$ g/mouse of pNGVL4a-CRT/E7 DNA via intramuscular injection follow by electroporation at different site on day 4 and boosted once 4 days later. (A) Bioluminescence images of the cervicovaginal TC-1/luciferase tumor-bearing mice. (B) Kaplan-Meier survival of the TC-1/luciferase tumor-bearing mice.

As shown in Figure 3, tumor bearing mice that received hind leg vaccination demonstrated a significantly greater reduction in luminescence signal as compared to the tumor bearing mice vaccinated at the front leg or tumor bearing mice with no vaccination, corresponding to a greater reduction in tumor volume. Furthermore, 100% of the tumor bearing mice with hind leg vaccination survived for at least 80 days while 80% of the tumor bearing mice with front leg vaccination and 100% of the tumor bearing mice with no vaccination died within 50 days after tumor challenge, demonstrating a significantly better anti-tumor effect against cervicovaginal tumor elicited by the therapeutic vaccination when administered at the hind leg of the tumor bearing mice.

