### 12.4 Early Stopping Rules

This study will evaluate two different sites of TA-CIN vaccine to determine the safety

and effectiveness of TA-CIN in patients with a history of advanced cervical cancer. For each injection site, the SAE rate of 20% or more is deemed unsafe. A total of 15 patients will be enrolled, with 7-8 patients in each injection site cohort.

The study will be stopped early if there are more than two patients with SAEs observed during the study. If the SAE rate is 20% or more, there is at least 55% chance to stop the study early with 15 patients.

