## **12.5 Statistical Analysis**

Adverse events will be tabulated by type and grade for each dose cohort.

The measure of immune response to the regimen will be the number of antigen-specific T cells detected by ELISPOT and/or ICC, or the simulation index of T cell proliferation, and the titer of the serum antibody as determined by ELISA. Each patient will have one measurement at baseline and 5 measurements at 5 time points after treatment. Descriptive statistics (mean and SD) and box plots will be used to summarize the immunogenicity by time point and dose cohort. Formal hypothesis testing will not be conducted to determine the ideal vaccination site. Instead, a “winner” will be picked based on the observed number of responses (42). Two-sample t-test will be used to compare the immunogenicity between two immunization sites. Data transformation will be applied if the distribution is not normal. In addition, the time course of outcomes will be investigated graphically by individual subject plots.

Cox regression analysis will be conducted to explore the association between time to disease recurrence and vaccine-induced immune response status. Patient baseline characteristics including disease stage and history of treatment will be adjusted in the analysis.

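### Section 1 says clinical response will be evaluated in the two injection-site cohorts, but Section 12.5 summarises neither recurrence nor plasma HPV16 DNA by site and gives objective 2.3.3 no analysis (minor)

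*Combined protocol and SAP*

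**What the plan says.** Section 1 opens its list of evaluations with "Patient immune and clinical responses in cohorts with different injection sites will be evaluated through the following methods". Item 3 is "3) plasma for residual HPV viral load" and item 4 is "imaging scans per standard-of-care (i.e., every 6-12 months) and as clinically indicated to assess time to disease recurrence". Section 12.4 describes the study of the two sites as determining safety "and effectiveness of TA-CIN in patients with a history of advanced cervical cancer".

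Section 2.3 makes both measures exploratory. Objective 2.3.3 is "To assess residual HPV16 viral load in plasma", with no comparator. Objective 2.3.4 links time to recurrence to vaccine-induced immune responses, not to site.

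Section 12.5 tabulates adverse events and summarises immunogenicity by cohort. It calls these dose cohorts. With one dose level, I read this as the two site groups of Section 6.3. The winner is picked on the number of immune responses, and the t-test compares immunogenicity. For recurrence the plan is: "Cox regression analysis will be conducted to explore the association between time to disease recurrence and vaccine-induced immune response status", adjusted for baseline characteristics that include stage and treatment history. Injection site is not named in that model. Plasma DNA appears in neither 12.1 nor 12.5, although Section 9.1.4 quantifies it by PCR.

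**The concern.** Injection site is the only randomised factor (Section 6.2). A summary by site is the one description of recurrence and plasma DNA in this trial that randomisation protects from systematic bias, and Section 1 leads the reader to expect it. Plasma DNA is collected at seven points on the calendar and then goes unused.

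The recurrence analysis that is planned rests on a weaker contrast. Response status is not randomised and is known only after dosing. Section 12.1 defines it from the maximum increase after administration, so a patient with more evaluable visits has more chances to qualify. A reader could take a responder hazard ratio below 1 as vaccine benefit when part of it comes from the definition.

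The rationale for comparing sites also rests partly on tumour control. Section 3.7.2 reports the mouse result as "demonstrating a significantly better anti-tumor effect against cervicovaginal tumor elicited by the therapeutic vaccination when administered at the hind leg".

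**Working it through.** **1. The plan's own figure.** The only figure for the site comparison is in Section 12.2: about 70% chance of picking the better site at 65% versus 45% response, 7 per group. P(X_A > X_B) for two independent binomials, with ties counted as failures, is 0.693. At 60% versus 45% it is 0.621, against about 60% stated. Both figures hold, and both concern immune response only. No figure is given for recurrence or plasma DNA.

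**2. What 12.5 covers.**

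| Measure | Section 1 | Objective | By site in 12.5 | Other analysis in 12.5 |
|---|---|---|---|---|
| Immune assays | yes | 2.2 | yes | individual plots |
| Plasma HPV16 DNA | yes, item 3 | 2.3.3 | none | none named |
| Time to recurrence | yes, item 4 | 2.3.4 | none | Cox on response status |

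Plasma draws in Section 10: Pre-Study, Weeks 5, 9 and 11-13, and Months 6, 12 and 24, which makes 7 (one baseline, six after dosing). The fourth follow-up draw is Month 6.

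**3. Guaranteed-time bias.** Assumptions, none from the documents: no vaccine effect; 30% recur by Month 24 at a constant hazard, so S(t) = 0.70^(t/24); draws at months 1, 2, 2.75, 6, 12 and 24; draws stop at recurrence; a patient with all m visits has a 45% chance of response, so with k visits the chance is 1 − 0.55^(k/m).

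| Recurrence between months | Probability | Response, m = 4 | Response, m = 6 |
|---|---|---|---|
| 0 and 1 | 0.0148 | 0 | 0 |
| 1 and 2 | 0.0145 | 0.139 | 0.095 |
| 2 and 2.75 | 0.0108 | 0.258 | 0.181 |
| 2.75 and 6 | 0.0453 | 0.361 | 0.258 |
| 6 and 12 | 0.0780 | 0.450 | 0.329 |
| 12 and 24 | 0.1367 | 0.450 | 0.392 |
| none by 24 | 0.7000 | 0.450 | 0.450 |

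- m = 4: responders who recur 0.118, all responders 0.118 + 0.315 = 0.433. Recurrence is 0.118/0.433 = 27.2% in responders and (0.300 − 0.118)/0.567 = 32.1% in non-responders.
- m = 6: 0.094/0.409 = 23.0% against (0.300 − 0.094)/0.591 = 34.8%.

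Simulated Cox models under this null give hazard ratios of about 0.78 (four visits) and 0.57 (six). If draws continue on schedule after recurrence, status is independent of recurrence and this bias disappears. The documents do not say which applies. Section 12.1 counts four follow-up measurements, Section 12.5 five, and the calendar six.

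**4. Residual confounding.** Assume half the patients have 15% and half 45% recurrence, with no vaccine effect. Responders' recurrence = (r₁ × 0.15 + r₂ × 0.45)/(r₁ + r₂), where r₁ and r₂ are the response rates in the two halves. HR = ln(1 − responder rate)/ln(1 − non-responder rate).

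| r₁, r₂ | Responders | Non-responders | HR |
|---|---|---|---|
| 65%, 45% | 27.3% | 33.3% | 0.79 |
| 65%, 35% | 25.5% | 34.5% | 0.70 |
| 45%, 65% | 32.7% | 26.7% | 1.28 |
| 35%, 65% | 34.5% | 25.5% | 1.44 |

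The direction depends on which half responds better, and the documents do not settle that. These values are unadjusted. By randomised site both groups expect 30%.

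**5. What a by-site summary can show.** The exact 95% interval for 2 of 7 is 3.7% to 71.0%. With 30% true recurrence at both sites and 7 versus 8 patients, observed rates differ by at least 20 points in 39% of trials and by at least 30 points in 24%. Power of a log-rank test is Φ(|ln HR|√d/2 − 1.96). For HR 0.5 it runs from 7% (2 events) to 27% (all 15 recur). Reaching 80% needs 4(1.96 + 0.84)²/(ln 0.5)², which is 66 events. Only a descriptive summary is sensible.

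**The case against.** The strongest reply is that 12.5 does what objective 2.3.4 asks. That objective ties recurrence to immune response, and the Cox model is labelled exploratory. No objective sets a comparison of recurrence between sites, Section 1 says evaluated and not compared, and effectiveness in 12.4 stands in a stopping-rule section and names no tumour outcome. All of this stands. It limits the point to a mismatch between Section 1 and 12.5, plus an objective (2.3.3) with no analysis. It does not remove it, because 12.5 lacks even a by-site description.

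The model also adjusts for stage and treatment history. That may remove part of the confounding in step 4, and treatment history might include time since treatment, though 12.5 does not say so. Adjustment for baseline factors does not address guaranteed-time bias.

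The sentence on graphing the time course of outcomes might be read as covering plasma DNA. It follows the immunogenicity text, names no DNA measure and concerns individual plots.

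Three stronger readings are tempting, and the documents support none of them:

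- *Confounding will make responders look protected.* The net direction is unknown. Section 12.2 expects prior treatment to prime the response, and if priming is strongest soon after treatment the confounding could reverse.
- *The site is wrongly chosen without recurrence.* Section 1 deliberately bases selection on immunogenicity combined with toxicity.
- *A by-site difference could be large enough to detect.* Fisher's test at 0% versus 80% with 7 versus 8 patients would reject in 94% of trials. Those rates are mouse deaths with active tumour under a different vaccine, a DNA vaccine given with electroporation. The patients here have no evidence of disease.

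**Conclusion.** The point holds as a minor gap. Section 1 announces clinical evaluation in the site cohorts, 12.5 provides none, and objective 2.3.3 has no analysis. These are matters of text and need no assumption.

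The recurrence analysis that does exist rests on a status determined after dosing. Under the assumptions of step 3 the null hazard ratio is about 0.78 or 0.57, depending on how many visits define response, and it returns to 1 if draws continue after recurrence. Residual confounding could push it either way.

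A reader might infer that the trial omits a randomised comparison it was designed to make. It does not: both measures are exploratory, and the primary endpoint and site selection are unaffected.

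**What to change.** Add to Section 12.5, before the Cox sentence:

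*In all dosed patients, by randomised injection site and without hypothesis testing: number with recurrence by Month 24 with exact 95% confidence interval; Kaplan-Meier curves from first dose; and detectable plasma HPV16 DNA (n/N) and its level at baseline and each visit. These summaries are reported alongside the site selection and are not a criterion for it.*

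The last sentence matters for timing. If the site is selected on the fourth follow-up measurement (Month 6), Month 24 recurrence is not available for another 18 months.

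Keep the Cox model, call it a supportive, non-randomised association, and either fix response status at a landmark or enter it as time-dependent. A Month 6 landmark would drop patients who recur earlier: 1 − 0.70^(6/24) = 8.5% under the assumption above, about 1 of 15. A time-dependent status keeps them. Counting time from the end of definitive treatment with delayed entry is optional and does not replace this step.

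If the sponsor does not want the by-site summary, Section 1 should drop its by-site clinical wording. Section 12.5 would still need a line for objective 2.3.3.

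The cost is a few sentences, one table and one figure, from data already collected. The drawback is very wide intervals, which the descriptive label covers.

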## 2. OBJECTIVES

### 2.1 Primary Objectives

- 2.1.1 To determine the safety and feasibility of intramuscular administration of TA-CIN vaccine via arm or thigh in patients with a history of HPV16 associated IB1-IV cervical cancer

### 2.2 Secondary Objectives

- 2.2.1 To evaluate the levels of circulating antibody to HPV16 E6, E7, and L2 in the peripheral blood pre- and post-vaccination by ELISA
- 2.2.2 To evaluate the levels of circulating HPV16 E6- and E7- specific CD8+ T cells and/or CD4+ T cells in the peripheral blood pre- and post-vaccination using the ELISPOT assay and/or cell surface staining with multi-parameter flow cytometry analysis
- 2.2.3 To evaluate the proliferative responses of peripheral blood mononucleocytes pre- and post-vaccination in response to stimulation by HPV16 E6, E7 and L2

### 2.3 Exploratory Objective(s)

- 2.3.1 To evaluate the levels of circulating HPV16 E6- and E7-specific CD8+ T cells in the peripheral blood pre- and post-vaccination using T cell receptor sequencing
- 2.3.2 To evaluate the levels of HPV-specific neutralizing antibodies in the peripheral blood pre- and post-vaccination
- 2.3.3 To assess residual HPV16 viral load in plasma
- 2.3.4 To assess time to disease recurrence as a measure of clinical response that may be associated with vaccine-induced immune responses

## 3. BACKGROUND

### 3.1 Cervical Cancer

Globally, cervical cancer accounted for an estimated 530,000 new cancer cases worldwide and for 275,000 deaths in 2013 (1). The most common histologic types of cervical cancer are squamous cell (69 percent of cervical cancers) and adenocarcinoma (25 percent). In countries that do not have access to cervical cancer screening and prevention programs, cervical cancer remains the second most common type of cancer and cause of cancer deaths among all types of cancer in women (2). In the United States (U.S.), an estimated 12,000 women diagnosed with cervical cancer each year (3). It is less common in the U.S. because of the routine use of Pap smear testing in intervention via ablation on high grade cervical intraepithelial neoplasia (CIN). Prior to the introduction of the Pap test in the 1940s, cervical cancer was one of the leading causes of

cancer death for women in the United States. But after routine cervical cancer screening was initiated, cervical cancer incidence was reduced by 70 percent and deaths from cervical cancer by 90 percent. Despite treatment advances over the past several decades including radiotherapy, cisplatin-based chemotherapy and/or surgery, the overall 5-year survival in the U.S. has not changed significantly and remains approximately 30% (<http://www.cancer.org/Cancer/CervicalCancer/DetailedGuide/cervical-cancer-survival>). The human papillomavirus (HPV) is central to the development of cervical dysplasia and cancer is detected in 99.7 percent of cervical cancers.

### **3.2 Human Papillomavirus as an Etiologic Factor in a Distinct Subset of Cervical Cancers**

Human papillomaviruses (HPV) are small, non-enveloped DNA viruses that induce self-limited epithelial lesions of the skin or mucosa. Of the more than 150 genotypes of HPV that have been identified, a dozen have been found to induce lesions that may progress to cancer. Persistent infection with one of about 14 genotypes of carcinogenic human papillomavirus (HPV) causes almost all cases, and 70% of cervical cancer cases in the U.S. are associated with HPV 16 or 18 (4). The International Agency for Research on Cancer (IARC) concluded that there is sufficient evidence in humans to establish the carcinogenicity of HPV in causing cervical cancer and a subset of head and neck cancers. HPV DNA has been detected in the tumor nuclei of up to approximately 99% of all cervical cancers. HPV type 16 (HPV16) is the most prevalent HPV type detected in cervical cancers, involved in approximately 50-60%. Given the causative role of HPV16 in at least half of cervical cancer cases, prophylactic vaccines targeting HPV16 have been developed for the prevention of HPV-related cervical malignancies. Unfortunately, the licensed preventive HPV vaccines (Gardasil® and Cervarix®) have no documented therapeutic activity for the treatment of cervical cancer. Therefore, there is an urgent need for new targeted treatments for cervical cancer to complement existing modalities such as radiation and/or cisplatin chemotherapy.

